10.0 DRUG INFORMATION

10.1 Aspirin or Aspirin-Matched Placebo

Aspirin/Placebo is IND exempt as used in this trial. This exemption has been determined by attestation that neither the investigator nor sponsor intends to seek a new indication for use or to support any other significant change in the labeling or product advertising for aspirin. This investigation will use an approved route of administration and dosage of aspirin and has no factors that increase the risk of the product. This investigation will be in compliance with 21CFR parts 56, 50, and 312.7 and neither the investigator nor the sponsor will promote or represent that aspirin is safe or effective for the context that is under investigation in this study. This investigation will not commercially distribute or test market the study agent, and will not unnecessarily prolong an investigation.

Procurement

Aspirin/placebo is an investigation agent supplied by Bayer and distributed by McKesson. Use the order form that is provided on the A011502 study page of the Alliance and CTSU web sites to order Aspirin/placebo. McKesson will ship a maximum of 2-year supply per shipment per patient to the site.

At the end of the trial, any expired or remaining supplies of study drug should be destroyed according to institutional procedure.

Formulation

Aspirin/placebo is supplied as matching tablets in 300 mg and 100 mg strength in 200 count bottles. Please see drug order form for further details regarding supply.

Aspirin 300mg tablets contain: 300mg acetylsalicylic acid, 30 mg powdered cellulose, 30mg maize starch, with coating of methacrylic acid-ethylacrylate copolymer, polysorbate 80, sodium laurilsulfate, talc, and triethyl citrate. Appearance is round coated white tablet 10mm in diameter and 407mg in weight.

Placebo 300mg tablets contain: 36mg calcium hydrogen phosphate dihydrate, 72mg microcrystalline cellulose, 15mg anhydrous citric acid, 198mg lactose monohydrate, 1mg magnesium stearate, 36mg maize starch, and 2mg colloidal anhydrous silica, with coating of methacrylic acid-ethylacrylate copolymer, talc, and triethyl citrate. Appearance is round coated white tablet 10mm in diameter and 407mg in weight.

Aspirin 100mg tablets contain: 100mg acetylsalicylic acid, 10 mg powdered cellulose, 10mg maize starch, with coating of methacrylic acid-ethylacrylate copolymer, polysorbate 80, sodium laurilsulfate, talc, and triethyl citrate. Appearance is round coated white tablet 7mm in diameter and 137mg in weight.

Placebo 100mg tablets contain: 12mg calcium hydrogen phosphate dihydrate, 24mg microcrystalline cellulose, 5mg anhydrous citric acid, 66mg lactose monohydrate, 0.4mg magnesium stearate, 12mg maize starch, and 0.67mg colloidal anhydrous silica, with coating of methacrylic acid-ethylacrylate copolymer, talc, and triethyl citrate. Appearance is round coated white tablet 7mm in diameter and 137mg in weight.

Storage and Stability

Store aspirin and placebo at room temperature 20° to 25°C (68° to 77°F), with excursions permitted to 15°C to 30°C (59°F to 86°F)."

Administration

Aspirin should be administered with food or full glass of water to minimize GI distress. Do not crush enteric coated tablets.

Reconciliation

Utilize the NCI oral DARF for documentation. Forms should be study specific and patient specific due to the double blind nature of the trial.

Drug Interactions

Aspirin is a minor substrate of CYP2C9. Inhibitors and inducers of CYP2C9 may alter aspirin exposure. Aspirin has the potential to have the following drug interactions:

Angiotensin converting enzyme (ACE) inhibitors: The hyponatremic and hypotensive effects of ACE inhibitors may be diminished by concomitant administration of aspirin.

Acetazolamide: Concurrent use of aspirin and acetazolamide can lead to high serum concentrations of acetazolamide (and toxicity) due to indirect effects on the renin-angiotensin conversion pathway.

Anticoagulant/Antiplatelet therapy: Patients on concomitant anticoagulant and antiplatelet therapies are at increased risk of bleeding with concomitant aspirin due to competition at the renal tubule for secretion.

Anticonvulsants: Salicylates can displace protein-bound phenytoin and valproic acid, leading to decreases in phenytoin and valproic acid concentrations.

Beta blockers: The hypotensive effects of beta blockers may be diminished with concomitant aspirin due to inhibition of renal prostaglandins, leading to decreased renal blood flow and salt/fluid retention.

Diuretics: Diuretic effectiveness may be diminished with concurrent aspirin due to inhibition of renal prostaglandins, leading to decreased renal blood flow, and salt and fluid retention.

Methotrexate: Salicylate can inhibit renal clearance of methotrexate, leading to bone marrow toxicity, especially in the elderly or renally impaired.

Nonsteroidal Anti-Inflammatory Drugs (NSAIDs): Concomitant administration of NSAIDs and aspirin may lead to increased bleeding or decreased renal function. Avoid concurrent use.

Oral Hypoglycemics: Moderate aspirin doses may increase the effectiveness of oral hypoglycemic agents causing hypoglycemia.

Uricosuric Agents: (Probenecid and Sulfinpyrazone): Salicylates antagonize the uricosuric action of uricosuric agents.

Pharmacokinetics

Absorption: Immediate, rapid and completely absorbed from gastrointestinal tract.

Distribution: Widely distributed to all tissues and fluids in the body including the central nervous system (CNS) and breast milk and fetal tissues. The highest concentrations are found in the plasma, liver, renal cortex, heart and lungs. The protein binding of salicylate is concentration-dependent, i.e. non-linear.

Metabolism: Hydrolyzed to salicylate (active by esterases in GI mucosa, red blood cells, synovial fluid and blood; metabolism of salicylate occurs primarily by hepatic conjugation; metabolic pathways are saturable).

Excretion: Urine (75% as salicyluric acid, 10% as salicylic acid).

T1/2: Parent drug 15 to 20 minutes; Salicylates 3 hours.

Adverse Events

Cardiovascular: Cardiac arrhythmia, edema, hypotension, tachycardia.

Central Nervous System: Agitation, cerebral edema, coma, confusion, dizziness, fatigue, headache, hyperthermia, insomnia, lethargy, nervousness, Reye's syndrome.

Dermatologic: Skin rash, urticarial.

Endocrine & Metabolic: Acidosis, dehydration, hyperglycemia, hyperkalemia, hypernatremia (buffered forms), hypoglycemia (children).

Gastrointestinal: Gastrointestinal ulcer, duodenal ulcer, dyspepsia, epigastric distress, gastritis, gastrointestinal erosion, heartburn, nausea, stomach pain, vomiting.

Genitourinary: Postpartum hemorrhage, prolonged gestation, prolonged labor, proteinuria, stillborn infant.

Hematologic & Oncologic: Anemia, blood coagulation disorder, disseminated intravascular coagulation, hemolytic anemia, hemorrhage, iron deficiency anemia, prolonged prothrombin time, thrombocytopenia.

Hypersensitivity: Anaphylaxis, angioedema.

Neuromuscular & Skeletal: Acetabular bone destruction, rhabdomyolysis, weakness.

Otic: Hearing loss, tinnitus.

Renal: Increased blood urea nitrogen, increased serum creatinine, interstitial nephritis, renal failure (including cases caused by rhabdomyolysis), renal insufficiency, renal papillary necrosis

Respiratory: Asthma, bronchospasm, dyspnea, hyperventilation, laryngeal edema, noncardiogenic pulmonary edema, respiratory alkalosis, tachypnea.

Miscellaneous: Low birth weight.

Postmarketing and/or case reports (Limited to important or life-threatening): Anorectal stenosis (suppository), atrial fibrillation (toxicity), cardiac conduction disturbance (toxicity), cerebral infarction (ischemic), cholestatic jaundice, colitis, colonic ulceration, coronary artery vasospasm, delirium, esophageal obstruction, esophagitis (with esophageal ulcer), macular degeneration (age-related), periorbital edema, rhinosinusitis.

- Nursing Guidelines
- 1. Patients may experience GI upset and or reflux. Treat symptomatically and monitor for effectiveness.
- 2. Aspirin can cause GI bleeding. Instruct patients to report any black tarry stools and/or hematemesis to the study team immediately.
- 3. Patients may experience increased bruising and/or bleeding. Instruct patients to report this to the study team.
- 4. Patients should be instructed not to take NSAID's in conjunction with aspirin. Concomitant use can lead to increased risk of bleeding and/or renal dysfunction.

10.2 Shipment of Study Drug Supply Directly to the Study Participant

Sites may ship a study participant's drug supply directly to the participant's place of residence if a site so chooses. The costs associated with the shipping of the participant's drug supply to their place of residence are the sole responsibility of the site. The Alliance will not reimburse a site for this cost.

McKesson will ship a maximum of 2-year supply per shipment per patient. Sites may distribute all or a portion of this supply to the participant. If a site were to elect to ship directly to the participant's place of residence, the Alliance recommends shipping the first of 6 months' supply. Subsequent 6 month supplies can be distributed directly to the participant during "scheduled "patient visits (see Study Calendar, Section 5.0).

Participants should be informed about storage requirements per protocol, Section 10.2, namely:

"Store Aspirin/Placebo at 15° to 30°C (59° to 86°F) in a dry place and keep the container tightly closed."

11.0 MEASUREMENT OF EFFECT

11.1 Evaluation of Breast Cancer Outcomes

Disease will be monitored according to ASCO guidelines [22]. The diagnosis of a first breast cancer recurrence or second primary can be made only when both the clinical and laboratory findings confirm the presence of disease. Suspicious findings do not constitute criteria for breast cancer recurrence. PET scans may be performed at the discretion of the investigator. However PET scans, in the absence of objective findings on CT, MRI, or other imaging studies do not meet the criteria of an acceptable method of determining breast cancer recurrence for this study. Any recurrence of malignant disease should be proven by biopsy whenever possible. Treatment of a breast cancer recurrence or second primary cancer will be at the discretion of the treating physician.

For all confirmed breast cancer recurrence or second primary cancers, the time to event will be based on the earliest date of diagnostic evidence. Initial diagnosis of the event should not be a first occurrence of symptoms, but must be based on a clinical assessment with objective findings, whether by physical exam or radiological determination that is subsequently confirmed (if applicable) as defined below.

11.1.1 Invasive ipsilateral breast cancer recurrence

Defined as evidence of invasive cancer in the ipsilateral breast or chest wall. Patients who develop clinical evidence of tumor recurrence in the remainder of the ipsilateral breast or chest wall must have a biopsy of the suspicious lesion to confirm the diagnosis.

11.1.2 Invasive local/regional recurrence

Defined as the development of invasive tumor in the ipsilateral internal mammary, ipsilateral supraclavicular, ipsilateral infraclavicular, and/or ipsilateral axillary nodes, as well as the soft tissue of the ipsilateral axilla. This can be confirmed with positive cytology or histologic biopsy.

11.1.3 Distant recurrence

Defined as evidence of invasive tumor in any areas of the body, with the exception of those defined as local or regional recurrence above.

11.1.4 Invasive contralateral breast cancer

Defined as evidence of invasive breast cancer in the contralateral breast or chest wall. This must be confirmed histologically.

11.1.5 Second primary invasive cancer (non-breast)

Defined as evidence of any non-breast second primary invasive cancer, excluding squamous or basal cell carcinoma of the skin and in situ carcinomas of any site. This must be confirmed histologically whenever possible.

11.2 Definitions of Analysis Variables

Formal definitions of variables used in analyses can be found in the Statistical Considerations section of the protocol.

11.3 Evaluation of Cardiovascular Outcomes

11.3.1. Myocardial infarction

Both non-fatal and fatal myocardial infarctions are to be reported. Standard CTCAE adverse event definitions will be used.

11.3.2. Cerebrovascular event

Both fatal and non-fatal cerebrovascular events are to be reported. The definition of a cerebrovascular event will be based upon radiographic evidence of an ischemic or hemorrhagic stroke.

11.3.3 Need for cardiovascular procedures

All cardiovascular procedures including coronary artery bypass surgery, coronary stent placement, and/ angioplasty of coronary vessels are to be reported.

12.0 END OF TREATMENT/INTERVENTION

12.1 Duration of Treatment

12.1.1 Protocol treatment is for 5 years or until the first occurrence of invasive disease, as follows: Distant recurrence, locoregional recurrence, ipsilateral or contralateral breast cancer, second primary (non-breast) invasive cancer, or death from any

cause. Treatment after any of these events is at the discretion of the treating physician. (See [Section 7.0 Treatment Plan](#)).

12.1.2 Early discontinuation of study agent

If protocol treatment is discontinued early for reasons other than patient death or the invasive disease events listed above, such as, adverse events from A011502 protocol therapy, physician discretion, patient withdrawal, early unblinding or extraordinary medical circumstances, continue to follow the patient according to [Section 12.2](#).

12.2 Patient Follow-up

Follow all patients enrolled on this study regardless of eligibility status, including those who do not receive any protocol therapy, or switch to non-protocol therapy, for a maximum of 10 years.

- Patients who complete five years of study treatment without a disease event will be followed annually for 10 years from registration for invasive disease events (locoregional and distant recurrence and new primaries in breast and non-breast sites) and survival.
- Patients who stop treatment before five years without a disease event will have a follow-up visit 6 months after end of protocol treatment, and then will be followed annually for 10 years from registration for invasive disease events (locoregional and distant recurrence and new primaries in breast and non-breast sites) and survival.
- Patients who stop treatment before five years due to a disease event will be followed annually for 10 years from registration for invasive disease events (locoregional and distant recurrence and new primaries in breast and non-breast sites) and survival.

Reports of all invasive disease events, i.e., first and subsequent, and survival are to be submitted yearly for the 10-year follow-up period.

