2.2 Secondary Objectives

2.2.1 To compare the effect of aspirin versus placebo in early stage HER2 negative breast cancer patients upon:

- a) Distant disease-free survival
- b) Overall survival
- c) Cardiovascular disease (see [Section11.3](#))

2.2.2 To compare the toxicity of aspirin versus placebo in early stage HER2 negative breast cancer patients.

2.2.3 To assess adherence to aspirin and placebo among early stage HER2 negative breast cancer patients.

2.2.4 To bank tumor and germline deoxyribonucleic acid (DNA), plasma and urine collected at baseline and sequential plasma and urine collected 2 years later for future measurement of inflammatory markers.

2.2.5 To determine if there are subgroups of participants characterized by lifestyle factors associates with greater inflammation for whom there is greater benefit of aspirin versus placebo upon iDFS.

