5.0 STUDY CALENDAR

The Pre-study testing interval is a guideline only. Laboratory and clinical parameters during treatment are to be followed using individual institutional guidelines and the best clinical judgment of the responsible physician. It is expected that patients on this study will be cared for by physicians experienced in the treatment and supportive care of patients on this trial.

Pre-Study Testing Intervals

- To be completed \leq 28 DAYS before registration: History and physical.

	Prior to Registration/ Randomization	Every 6 months from start of study treatment +/- 28 days*	At End of protocol Treatment	Post treatment follow-up
Tests & Observations				
History and Progress Notes	X	X	X (4)	X
Physical Examination	X	X	X (4)	X
Weight, BMI	X(1)	X (1)		
PS	X	X	X	
Height	X			
Pulse, Blood Pressure	X	X		
Adverse Event Assessment	X	X	X	
Patient Medication Diary		X (2)		
Evaluation of Disease Recurrence or new invasive disease		X (3)	X (4)	X (4)
For patients who agree to participate				
Lifestyle Measures of Inflammation assessments and Registration Fatigue and Uniscale Assessment	See Section 6.2			
Tissue, Blood and Urine samples for Future use	See Section 6.3. (5)			

*The first 6-month visit should be timed from the start of treatment. Subsequent visits should be timed based on the date of the previous visit.

1. BMI to be calculated at baseline and at 24 months.
2. The Patient Medication Log must begin the day the patient starts taking the study medication and must be completed per protocol and returned to the treating institution at each 6 month visit (see [Section 7.0](#)).
3. Patients should be evaluated for disease recurrence every 6 months while receiving study treatment according to [Section 11.1](#).

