4. Patients who complete five years of study treatment will be followed annually (+/- 28 days) until 10 years from registration. Patients who stop treatment before 5 years without an invasive disease event will have a follow-up visit 6 months (+/- 28 days) after end of protocol treatment and then followed annually (+/- 28 days) until 10 years from registration. Patients who stop treatment before 5 years due to an invasive disease event may receive treatment at physician discretion and will be followed annually (+/- 28 days) until 10 years from registration. All patients will be followed for all invasive disease events (locoregional and distant recurrence and new primaries in breast and non-breast sites) and survival for a maximum of 10 years from registration.
5. Sample should be drawn after consent, prior to the start of treatment.

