13.3.2 Secondary Endpoint

Secondary endpoints for disease outcome include overall survival (OS) and distant disease free survival (DDFS). OS is defined as the time from randomization to death from any cause; surviving patients will be censored at the date last known to be alive. DDFS is defined as the time from randomization to the first occurrence of any one of the following events for invasive disease: Distant recurrence, second primary (non-breast) invasive cancer or death from any cause; censoring will occur at the date the patient was last known to be alive and free from distant invasive breast cancer and second invasive primaries.

Additional secondary endpoints include development of cardiovascular disease (including cerebrovascular events, myocardial infarction, or coronary artery disease requiring stent placement, angioplasty, or bypass surgery).

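### Cardiovascular disease is a secondary endpoint compared by arm, but the post-treatment schedule does not collect its non-fatal events

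*Combined protocol and SAP*

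**What the plan says.** **The endpoint.** Section 2.2.1 lists "c) Cardiovascular disease" among the outcomes compared between aspirin and placebo. Section 13.3.2 adds: "Additional secondary endpoints include development of cardiovascular disease". It defines this as cerebrovascular events, myocardial infarction, or coronary disease needing a stent, angioplasty or bypass. Neither section limits the endpoint to time on study drug.

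**The duty to report.** Section 11.3 covers the components one by one: "Both non-fatal and fatal myocardial infarctions are to be reported"; "Both fatal and non-fatal cerebrovascular events are to be reported"; "All cardiovascular procedures including coronary artery bypass surgery, coronary stent placement, and/ angioplasty of coronary vessels are to be reported". It names no form, visit or time window.

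**The follow-up schedule.** In the section 5.0 calendar, the row "Adverse Event Assessment" is marked before registration, every 6 months and at end of treatment, but not in the post-treatment column. There is no cardiovascular row. History and physical examination are marked post-treatment. Footnote 4 to the calendar says "All patients will be followed for all invasive disease events (locoregional and distant recurrence and new primaries in breast and non-breast sites) and survival", and section 12.2 repeats that content and closes with "Reports of all invasive disease events, i.e., first and subsequent, and survival are to be submitted yearly for the 10-year follow-up period".

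**The analysis.** Section 13.3.3 gives all secondary objectives a two-sided 0.05 test and Cox-based 95% intervals. It does not say how follow-up for the cardiovascular endpoint is censored.

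**The concern.** A site that follows the calendar and section 12.2 to the letter will ask stopped patients about cancer events and survival, and will have no scheduled prompt for a non-fatal infarction, stroke or coronary procedure. Treatment lasts at most 5 years and ends at the first invasive disease event, while follow-up runs to 10 years from registration, so every patient who remains in follow-up has some time off drug. Events not asked about at the time are hard to recover later.

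Two things are at stake for this endpoint. One is precision, because events are lost. The other is a possible imbalance in ascertainment, because time off drug may differ by arm: iDFS events stop treatment, and so do certain toxicities (8.2).

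**Working it through.** **Step 1: routes for a late non-fatal event.** Take a grade 3 or 4 myocardial infarction more than 30 days after the last dose, judged unrelated to study drug.

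- *Scheduled follow-up (5.0 footnote 4, 12.2):* not named.
- *Solicited list (9.1):* contains intracranial hemorrhage but not infarction, ischaemic stroke or coronary procedures, and is tied to baseline and treatment cycles.
- *Routine reporting, note (a) in 9.2:* marked for grades 3 to 5 at every attribution. It covers registration to 30 days after last treatment, or the Clinical Follow-Up Phase, a term the protocol does not define. If that phase means the whole post-treatment period, the event is reportable.
- *Routine reporting, note (b) in 9.2:* the form for events beyond 30 days after last treatment, marked only for possible, probable or definite attribution. Read alone, it does not take the event.
- *Expedited reporting (9.3.1, footnote 1):* beyond 30 days, possible or higher attribution only.
- *Section 11.3:* the event is to be reported, with no form or visit attached.

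A coronary procedure has no grade of its own, so it does not fit the 9.2 table. Fatal events have a route: 9.3 requires all deaths on study to be reported whatever the cause, and survival is followed to 10 years.

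**Step 2: reproduce the plan's event counts.** Inputs from 13.2: 5-year iDFS 77% on placebo, hazard ratio 0.75, 30-month accrual with a 6-month ramp to 108 per month (taken as linear), loss to follow-up 5% at 48 months, analysis at 54 months, 2936 patients (1468 per arm).

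- Placebo iDFS hazard: −ln(0.77)/60 = 0.004356 per month
- Aspirin iDFS hazard: 0.75 × 0.004356 = 0.003267 per month
- Loss hazard: −ln(0.95)/48 = 0.001069 per month

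Averaged over accrual, these give 216.4 placebo and 165.7 aspirin events, against 216 and 165 in section 13.5. Mean follow-up is 36.8 months.

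**Step 3: share of person-time off treatment at 54 months.** With stopping hazard s (iDFS hazard plus any other stopping hazard) and loss hazard l, a patient with potential follow-up x has expected follow-up (1 − e^(−lx))/l and expected on-treatment time (1 − e^(−(s+l)x))/(s+l). The off-treatment share is 1 minus the ratio of their averages over accrual. For iDFS stops only, mean on-treatment time is 33.84 months on placebo and 34.54 on aspirin, so the shares are 1 − 33.84/36.78 = 8.0% and 1 − 34.54/36.78 = 6.1%.

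The documents give no rate of stopping for other reasons, so a range is assumed (percent stopped by 5 years, constant hazard).

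**Step 4: upper bound on the effect.** Assume that every off-treatment event is missed, that the cardiovascular hazard is constant, and that unassessed time is counted as event-free. Then:

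- HR multiplier = (1 − aspirin share)/(1 − placebo share)
- interval widening on the log scale = 1/√(1 − pooled share)

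| Other stops by 5 years (placebo / aspirin) | Off-treatment share (placebo / aspirin) | Pooled share = events lost | HR multiplier | Interval widening |
|---|---|---|---|---|
| none | 8.0% / 6.1% | 7.0% | 1.021 | 1.037 |
| 20% / 20% | 14.1% / 12.4% | 13.3% | 1.020 | 1.074 |
| 40% / 40% | 21.2% / 19.7% | 20.4% | 1.019 | 1.121 |
| 20% / 30% | 14.1% / 15.9% | 15.0% | 0.980 | 1.085 |

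The direction of the shift depends on which arm has more time off drug. The first 30 days after the last dose are counted here as uncovered although note (a) covers them. Removing them lowers the first row's shares to about 7.6% and 5.8%.

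**The case against.** The strongest reply is that the duty to report already exists. Section 11.3 has no time or attribution limit, post-treatment visits include history and physical examination, and deaths are reported regardless of cause. This stands: late events are not excluded. What is missing is a form, visit or period that would make a site submit a non-fatal one.

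A reader might infer that the reporting routes contradict each other on attribution. The documents do not prove that. In the 9.2 table, note (b) can be read as an additional form for related late events, which leaves note (a) in force for unrelated ones. The filter in 9.3.1 footnote 1 governs expedited safety reporting only, where a narrower rule can serve a different purpose. What stands is an ambiguity caused by the undefined Clinical Follow-Up Phase.

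A reader might also infer that cardiovascular data are in fact being lost. The documents cannot show this, because section 6.1 places form timing in a separate Schedule of Forms that is not included. A cardiovascular item may already be on the follow-up form. In that case the protocol text still needs to say so.

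Lastly, a reader might measure the impact over the full 10 years, when years 5 to 10 are off treatment for everyone. The only final analysis the plan dates is the one at 381 iDFS events, expected at 54 months, so the longer horizon is not used here.

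**Conclusion.** The point holds as a gap between the endpoint and its collection schedule. The endpoint has no on-treatment limit, yet the calendar and section 12.2 do not schedule its collection after treatment, and the remaining route for non-fatal events is ambiguous.

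The effect at the planned analysis is modest. The bounds of about 7%, 13% or 20% of events lost use the protocol's own iDFS and loss rates, plus assumed other stops of 0, 20% or 40% and a constant cardiovascular hazard. The 2% shift in the hazard ratio also requires unassessed time to be counted as event-free. All of these overstate the real effect, because deaths and some late events will be reported. Precision is the main cost.

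Only this secondary endpoint is affected, not the primary iDFS analysis. The change is worth making because it is cheap and is most useful before follow-up accumulates.

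**What to change.** - **12.2, calendar footnote 4 and the post-treatment column:** add collection of the cardiovascular events that make up the 13.3.2 endpoint, as reported under 11.3, fatal or non-fatal, regardless of grade, attribution or treatment status, at each already scheduled follow-up visit, for all randomised patients.
- **9.2:** define Clinical Follow-Up Phase, and exempt these endpoint events from the grade and attribution filter.
- **11.3.3 and 13.3.2:** reconcile the two. The first covers all cardiovascular procedures, the second only a coronary list. State which procedures count towards the endpoint.
- **13.3.3:** state that the endpoint is censored at the last contact at which cardiovascular status was assessed, so that unassessed time is not counted as event-free. How death from other causes is modelled is the sponsor's choice.

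The cost is one short case report form item at visits that already include history and physical examination, plus text edits. No visit or procedure is added. If the Schedule of Forms already carries the item, the cost is text only.
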